5.2 Clinical Laboratory Assessments

5.2.1 Routine Assessments and Biomarkers

A list of all clinical laboratory tests that will be performed is provided in Table 1; the time points for sample collection are specified in the SOA.

Blood collected for standard haematology and serum chemistry (including coagulation parameters) will be analysed locally.

During Screening, if a subject's ALT or AST is greater than 3 x ULN, or a subject has elevated bilirubin or PT/INR, confirmatory testing will be completed. Abnormal safety labs at Screening can be repeated within 1 to 2 weeks. The difference between these 2 pre-treatment values for each abnormal laboratory parameter should differ by < 20% for each subject.

Efforts should be made by the Investigator to review subject medical history, concomitant medications and health status so that a clear explanation for the elevation is established. The Investigator, in consultation with the Sponsor, shall make a determination of subject eligibility based on review of Exclusion Criterion 8.

During the study, after treatment with SBC-103, in the event that a subject's ALT or AST is 2 x ULN (when baseline ALT or AST was within normal limits) or 3 x ULN (when baseline ALT or AST was greater than 1.5 x ULN), or when a subject has an elevation in bilirubin or PT/INR a confirmatory test should be completed at the earliest possible time point, but not later than the next scheduled visit. Upon positive confirmation of the elevated transaminases as described above, dosing will be paused until AST and ALT have returned to baseline or to study nadir (nadir values may be confirmed by additional laboratory sampling at the discretion of the Investigator, using the same laboratory for analysis of each sample), or normalised if the baseline level was within normal limits. See Section 6.2 for stopping rules.

Every effort will be made to collect urine for urinalysis testing. If urine can be collected, a urine pregnancy test will be performed and analysed locally for females of child-bearing potential. If a urine sample is not able to be provided, a serum pregnancy test will be performed and analysed locally.

Serum, and where possible, urine, will be collected for analysis of MPS IIIB substrate (total HS) and other disease-related biomarkers including NRE HS derivatives. CSF will be collected via lumbar puncture for analysis of total HS and other disease-related biomarkers including NRE HS derivatives. All efforts will be made to obtain a blood sample to evaluate serum albumin and serum IgG at the same time as the CSF sample, as reflected in the SOA. The CSF-AI will be calculated as the CSF albumin (mg/mL)/serum albumin (g/L). IgG index will be calculated as the ([CSF/serum IgG ratio] / [CSF-AI]). Refer to Section 5.2.1.3 for details regarding the lumbar puncture.

A specific sample for biomarker analysis is being collected in this study; however, remaining blood and urine samples collected in this study may also be used to analyse additional biomarkers of potential clinical interest, if there is sufficient sample and where local regulations permit. As subjects with MPS IIIB may be incontinent, urine samples for routine assessments and biomarkers may not be able to be collected, but should be attempted whenever possible.

Due to the limitations on the volume of blood collection that is considered to be acceptable in young children with very small total circulating blood volumes; see Committee for Medicinal Products for Human Use and Paediatric Committee guidance (EMEA/536810/2008, adopted 25 June 2009), the blood laboratory tests will be ranked by tier. Per individual, the study-related blood loss should not exceed 3% of the total blood volume during a period of 4 weeks and should not exceed 1% at any single time. The total volume of blood is estimated at 80 to 90 mL/kg body weight; 3% corresponds to about 2.4 to 2.7 mL blood per kg body weight.

Tier 1 assessments (see Table 1) are considered mandatory and all efforts should be made to collect these samples in all subjects. Samples for the Tier 2 or Tier 3 assessments will be collected if permitted based on the blood or CSF volume threshold for a subject's weight, as well as the subject's clinical status. All tests will be performed by a qualified laboratory.

Clinical laboratory samples will be stored by the Sponsor or designee in a secure and controlled environment until analysis, and will be destroyed by the Sponsor or designee after all worldwide obligations have been met, or sooner if required by local regulations.

Refer to the laboratory manual for further details regarding the collection, processing, and storage of clinical laboratory samples.

Page 53 of 104

Laboratory Parameter Panel	Tier	Local or Central Analysis	Matrix	Tests
Haematology	1	Local Lab	Whole blood	White blood cell count; red blood cell count; haemoglobin; haematocrit; MCV, MCH, MCHC; platelet count; neutrophils; lymphocytes; monocytes; eosinophils; basophils
Serum Chemistry	1	Local Lab	Serum	ALT, AST, alkaline phosphatase, GGT, albumin, total bilirubin, serum electrolytes (sodium, potassium, chloride, calcium, magnesium, phosphorus), glucose, creatinine, bicarbonate, total protein, blood urea nitrogen
Coagulation	1	Local Lab	Plasma	PT, INR
Urinalysis	N/A	Local Lab	Urine	pH, clarity, colour, specific gravity, glucose, ketones, blood, protein, nitrite, and leukocytes (microscopic examination will only be done if urinalysis is positive for blood, nitrite, or leukocytes, or if protein is > 1+)
Pregnancy test ^a	N/A	Local Lab	Urine	
MPS IIIB Diagnostics	1	Central Lab	Dried blood spot	NAGLU enzyme activity
РК	1	Central Lab	Serum	PK profile
РК	3	Central Lab	CSF	SBC-103 concentration
ADA	1	Central Lab	Serum	Anti-SBC-103 antibodies (IgM, IgG, and IgE). Subjects who experience a moderate or severe IAR should have a serum sample collected for ADA during the next study visit (≥ 4 days after the IAR) prior to the infusion.
	1	Central Lab	Serum	HS (total and NRE)
Biomarkers	2	Central Lab	Serum	Ferritin and chitotriosidase
	2	Central Lab	Plasma	Glutamic acid and glycine
	2	Central Lab	Serum	IgG, inflammatory markers, and biomarkers

Table 1:Clinical Laboratory Tests

Page 54 of 104

ALEXION PHARMACEUTICALS, INC. PROPRIETARY AND CONFIDENTIAL: DO NOT COPY OR DISTRIBUTE WITHOUT PERMISSION FROM ALEXION

Laboratory Parameter Panel	Tier	Local or Central Analysis	Matrix	Tests	
	N/A	Central Lab	Urine	HS (total and NRE)	
	1	Central Lab	CSF	HS (total and NRE)	
	2	Central Lab	CSF	HGF, calbindin D, Tau, pTau, amyloid β, albumin, IgG, glutamic acid and glycine	
	1	Central Lab	CSF/ Serum ^b	CSF/Serum Albumin Index (CSF-AI) and IgG index ([CSF/serum IgG ratio] / [CSF-AI])	
	2	Local Lab	CSF	Routine findings (cell counts, glucose, protein)	
Serum Tryptase	If clinically indicated	Central Lab	Serum	Subjects who experience a moderate of severe IAR should have a serum sample collected for analysis of tryptase 1-3 how after the IAR onset and another serum sample for tryptase and ADA during the next study visit (≥ 4 days after the IAR prior to the infusion.	

Table 1:Clinical Laboratory Tests

Key: ADA = anti-drug antibodies; ALT = alanine aminotransferase; AST = aspartate aminotransferase;
CSF = cerebrospinal fluid; CSF-AI = cerebrospinal fluid/serum albumin index; GGT = gamma-glutamyl transpeptidase; HGF = hepatocyte growth factor; HS = heparan sulphate; IAR = infusion-associated reaction; IgE = immunoglobulin E; IgG = immunoglobulin G; IgM = immunoglobulin M; INR= international normalised ratio; MCH = mean corpuscular haemoglobin; MCHC = mean corpuscular haemoglobin concentration; MCV = mean corpuscular volume; N/A = not applicable; NAGLU = alpha-N-acetylglucosaminidase; NRE = non-reducing end; PK = pharmacokinetics; PT = prothrombin time.

^a Test performed by a local laboratory for all female subjects of child-bearing potential. If a urine sample is not able to be provided, a serum pregnancy test will be performed by a local laboratory.

^b Ensure that serum albumin is collected at each time point a CSF sample is collected. If a serum chemistry is not scheduled at the same study visit, a serum albumin should be drawn.

5.2.1.1 Biomarkers

Blood samples for serum isolation will be obtained at the time points specified in the SOA for exploratory analyses to identify and evaluate disease-related biomarkers, where local regulations and blood volume threshold permits. A specific sample for biomarker analysis is being collected in this study; however, remaining blood or urine samples collected in this study may also be used to analyse additional biomarkers of potential clinical interest, if there is sufficient sample and where local regulations permit. These samples will be used to identify baseline disease and dynamic markers that will help the Sponsor to better understand the pathogenesis of MPS IIIB and related comorbidities and response to treatment. Given the rarity of MPS IIIB, the definitive list of analytes remains to be determined.

Collection of samples for biomarker analysis will be subject to discretionary approval from each centre's IRB/IEC and the specific written consent of the subject or the subject's parent or legal guardian. This section of the protocol only applies if approval for collection of these additional samples has been granted by the IRB/IEC and consent is provided by the subject (or the subject's parent or legal guardian).

Samples will be stored by the Sponsor, or designee, in a secure and controlled environment until analysis, and will be destroyed by the Sponsor or designee after all worldwide obligations have been met, or sooner if required by local regulations. Biomarker assays will be performed by a central laboratory or, as appropriate, by academic research laboratories with expertise in the analysis of specific biomarkers.

Refer to the laboratory manual for further details regarding the collection, processing, and storage of these samples.

5.2.1.2 Pharmacokinetic Assessments

As described in Table 2 and the SOA, blood samples will be collected to determine SBC-103 serum concentrations using an enzyme-based PK assay. PK samples collected concurrently with vital sign assessments will be taken prior to collection of blood pressure on the non-infusion arm. PK samples collected at all other time points will be taken at least 5 minutes following deflation of the blood pressure cuff. PK samples should not be taken from the same extremity where the infusion catheter is in place.

CSF samples for determination of SBC-103 concentration in the CSF may also be collected from subjects if CSF volume limitations based on subject's age and weight have not been exceeded.

	Day 0	Week 12	Week 24
Pre-infusion (within 30 minutes)	Х	X	Х
During Infusion			
5 minutes (±2 minutes)	Х		
10 minutes (±2 minutes)	Х		
30 minutes (±5 minutes)	Х	X	Х
50 minutes (±5 minutes)	Х		
70 minutes (±5 minutes)	Х		
90 minutes (±5 minutes) ^a	Х	X	Х
120 minutes/End of Infusion ^b (±5 minutes)	Х	Х	Х
After Completion of Infusion			
5 minutes (±2 minutes)	Х		
15 minutes (±2 minutes)	Х	X	Х
30 minutes (±5 minutes)	Х	X	Х
60 minutes (±5 minutes)	Х	X	Х
90 minutes (±5 minutes)	Х	X	Х
120 minutes (±5 minutes)	Х	X	X
4 hours (±5 minutes)	Х	X	Х
6 hours (±5 minutes)		X	
8 hours (±15 minutes)	Х		Х
12 hours (±15 minutes)	Х		Х
24 hours (±15 minutes) ^a	Х		Х

Pharmacokinetic Sampling Table 2:

^a Time points may be omitted, if necessary, to avoid exceeding blood volume limitations. ^b After the infusion bag has been emptied, but prior to the flush.

	Week 52	Week 78	Week 104	Week 130	Week 156
Pre-infusion (within 30 minutes)	X	Х	Х	X	X
During Infusion					
30 minutes (±5 minutes)	X		Х		X
90 minutes (±5 minutes) ^a	X		Х		X
120 minutes/End of Infusion ^b (±5 minutes)	X		Х		X
After Completion of Infusion					
30 minutes (±5 minutes)	X		Х		X
2 hours (±5 minutes)	X		Х		X
4 hours (±15 minutes)	X		Х		X
6 hours (±15 minutes)	X		Х		Х

Table 2 (continued): Pharmacokinetic Sampling

^a Time points may be omitted, if necessary, to avoid exceeding blood volume limitations.

^b After the infusion bag has been emptied, but prior to the flush.

5.2.1.3 Lumbar Puncture (Cerebrospinal Fluid)

Lumbar punctures will be performed for the collection of CSF at the time points specified in the SOA. The lumbar puncture may be performed under general anaesthesia, if clinically appropriate, or under light sedation and will be performed as per local practices by a qualified professional in accordance with local institutional procedures. The first 10 mL of CSF will be collected and mixed gently to avoid gradient effects. The actual volume may be adjusted based on subject age or size and local institutional guidelines. If CSF volume is limited, the analysis of CSF HS (total and NRE) should be prioritised as noted in Table 1.

Routine CSF findings will also be documented (e.g., cell counts, glucose, and protein levels), and MPS IIIB substrate (HS) and other CSF biomarkers will be analysed (see Table 1 for details).

Per the SOA, collection of serum chemistry will not always coincide with the collection of CSF. In order to measure the CSF-AI at each possible time point, a serum albumin sample should be collected at time points where a serum chemistry sample is not being collected at the same day as the CSF sample.

After the lumbar puncture is completed, the subject should be observed as per institution standard practice. Vital signs should be obtained prior to discharge. Any AEs or changes to concomitant medications should also be assessed.

5.2.2 Facial Dysmorphology Novel Analysis

Facial photographs will be obtained for FDNA at the time points specified in the SOA. This technology enables automatic detection and evaluation of subtle craniofacial dysmorphology associated with multiple rare diseases, by processing and analysing standard 2-dimensional facial photos. The FDNA system uses proprietary computer algorithms to recognise and describe subtle craniofacial malformations (out of a list of clinically relevant anatomical facial features) in mathematical terms. A ranked score, representing the probability of the genetic syndrome, is produced based on analysis of the severity of the facial alterations relative to variations in a normal population, as well as recognition of the face "gestalt" associated with certain rare diseases. FDNA offers potential as a tool for screening large populations for MPS IIIB, which may enable wider and earlier diagnosis of MPS IIIB patients, as well as providing a means for monitoring progression of disease in patients diagnosed with MPS IIIB. This study will evaluate FDNA technology as a means to evaluate both clinical characteristics and course of disease progression in MPS IIIB. FDNA assessment will be optional based on subject/parent consent to participate. A subject/caregiver may refuse this assessment and still participate in this study. Once a subject/caregiver consents to this assessment, all attempts should be made to collect data at each study time point.

5.2.3 General Anaesthesia/Sedation

Subject compliance and maintenance of appropriate and stable positioning during the MRI procedure is complicated due to the anticipated behaviour disturbances characteristic of MPS IIIB subjects. A key advantage of general anaesthesia is that it minimises any potential for stress or anxiety during the procedure and is independent of a subject's ability to cooperate, which is critical with MPS IIIB subjects. The whole process, including preparation and scan time, is more predictable, and the scan quality will benefit as a result of the subject being immobilised.

Thus, subjects will receive general anaesthesia prior to the MRI procedure. In principle all types of general anaesthesia techniques can be used as long as the subject is kept asleep during the MRI procedure. The decision should depend on comorbidities, anatomy, and fasting status in the individual case and the procedures and practices of the institution. In clinical practice and in earlier studies with subjects with MPS III, propofol sedation was used together with a laryngeal mask to guarantee a secure airway and to not unnecessarily prolong the procedure. The IV properties of propofol make it an ideal anaesthetic for subjects undergoing imaging assessments. An IV anaesthetic without endotracheal intubation allows for careful titration of sedation to achieve a clinical effect. Propofol provides the ability to titrate an anaesthetic level rapidly and maintain stable drug concentrations during the procedure, thus ensuring that anaesthesia is administered in a timely and consistent manner. Recovery from this type of anaesthesia is rapid and not accompanied by nausea or vomiting. Often the anaesthetic can be delivered allowing the subject to breathe spontaneously. Competency of airway is accomplished by the insertion of a laryngeal mask airway which allows ventilation of the subject in the cases required. Appropriate local procedures should be utilised under supervision of a paediatric anaesthesiologist, however, in subjects aged 1 to 10 years, a dose of 100 mcg/kg/min will be sufficient to keep the subject asleep with no movement during the scan. If the subject has an IV in place, then a bolus of 2 to 10 mg/kg (depending on age) can be given initially, followed by a continuous infusion of propofol.

If no IV is in place, then anaesthesia can be induced with an inhalative narcotic such as halothane or sevoflurane (with N₂O and oxygen), and IV can be inserted, and then continuous infusion of propofol started (Schulte-Uentrop, 2010, *Curr Opin Anaesthesiol*).

As indicated in Section 5.2.1.3, if clinically appropriate, lumbar punctures may also be performed under general anaesthesia in accordance with local institutional procedures. When applicable, the lumbar puncture should be performed just prior to the MRI scan and prior to dosing. Lumbar puncture, when not performed alongside the MRI scan, may also be performed under light sedation.

If clinically indicated, subjects may also receive general anaesthesia or sedation for central line placement for long-term vascular access, in accordance with institutional guidelines. When possible, the procedure to place the central line should be performed while the subject is already anaesthetised or sedated for another study procedure.

5.2.4 Structural and Diffusion MRI

MRI will be performed at the time points specified in the SOA.

High-resolution whole-brain T1-weighted and T2-weighted images will be acquired in order to enable measurements of brain volume and relative volumes of grey and white matter.

Whole-brain diffusion MRI will also be acquired with multiple diffusion sensitization orientations, b value ≥ 1000 s/mm². This will enable measurement of diffusion tensor parameters, including mean diffusivity (mean apparent diffusion coefficient) and fractional anisotropy, as well as anatomical connectivity mapping.

The estimated total scan time will be approximately 5 to 10 minutes for structural MRI sequences and 15 minutes for diffusion MRI sequences. All imaging scans will be read centrally. Detailed instructions on image acquisition and analysis will be provided in the Imaging Manual.

5.2.5 Telephone Calls

A follow-up telephone call will be made to each subject (or the subject's parent or caregiver) within 24 hours after each of the subject's second, third, and fourth doses to assess AEs.

At least 4 weeks after a subject's last dose of SBC-103 is administered, the subject (or the subject's parent or caregiver) will receive a follow-up phone call to assess AEs and concomitant medications unless the subject has a scheduled follow-up study visit.

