In addition, there is extensive human experience with ERTs for the treatment of other LSDs including: Gaucher's, Pompe, and Fabry diseases, MPS I and II (see Section 1.1.2). While these diseases have distinct clinical manifestations and demonstrate differences in the targeting and biological effects of the ERT, there are relevant data from these studies that inform the use of investigational products in this class. Substrate reduction, as evidenced by decreases in cerebrospinal fluid (CSF) GAG levels, has been demonstrated following intrathecal (IT) dosing in MPS IIIA and MPS II in ongoing clinical studies (Breen, 2013, *ASHG*, Wijburg, 2013, *Acta Paediatr*, Wijburg, 2013, *ACMHGM*, Muenzer, 2014, *LDN poster*). No new significant safety findings have emerged to date from these studies based on publically available data. Most of the adverse events (AEs) associated with clinical use of ERTs are comprised of infusion-associated reactions (IARs), which typically occur either during, or within 2 hours following completion of the infusion. Given the propensity for IARs with ERT administration, measures have been incorporated in this protocol to minimise risk to subject safety from such events (see Section 7.1.3).

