1.5.2 Risk/Benefit Assessment

As discussed in Section 1.1.1, MPS IIIB is a very rare disease that is associated with significant morbidity and mortality in affected patients. Currently, there are no safe or effective therapies for MPS IIIB.

Nonclinical studies conducted in the Sprague-Dawley rat and Cynomolgus monkey (including a 3-month study in juvenile monkeys) by IV route were generally well tolerated at the doses planned in this study. Minimal/mild microscopic findings were noted in the liver in some animals, and these changes appear to be limited and were seen at doses higher than planned in this study. Clinical observations such as decreased activity, drowsiness/sluggishness, decreased muscle tone, abnormal gait, and repetitive behaviour were noted generally after the third or fourth dose of SBC-103. These observations generally lasted for a short period of time and did not have any relationship with several tests performed using the blood and tissues (see Section 1.3). These findings along with anti-SBC-103 IgG antibodies are suggestive of hypersensitivity, which is not unexpected when administering a recombinant human protein to a heterologous species. It should be noted that nonclinical studies are not predictive of potential immunogenicity of humans (Brinks, 2011, *Pharm Res;* Ponce, 2009, *Reg Toxicol Pharmacol*).

Subjects in this clinical study will be monitored closely to identify any potential safety concerns, including monitoring liver parameters and antibody development. See Sections 5.2 and 6.2 for more details regarding laboratory assessments and subject stopping rules, respectively.

Extensive clinical experience with approved ERTs for other LSD indications is relevant for risk evaluation of SBC-103. The main AEs associated with administration of

Page 31 of 104

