3 INVESTIGATIONAL PLAN

3.1 Overall Design and Plan of the Study

This study (NGLU-CL01-T) is designed to evaluate the safety and tolerability of IV administration of SBC-103 for the treatment of MPS IIIB. Up to 5 subjects, previously enrolled in the NGLU-CL01 study at 1 centre in the United Kingdom, will be eligible to participate in this study. This interventional study will provide data on effects of treatment with SBC-103, and observational data in the absence of treatment in the same study subjects from study NGLU-CL01 to baseline of NGLU-CL01-T will be included in the analysis.

All subjects will initially receive 1 mg/kg SBC-103 IV qow. All subjects will be monitored in an in-patient setting for safety and tolerability for 24 hours following the first dose of SBC-103. The decision to continue dosing in each subject will be made by the Sponsor in consultation with the Principal Investigator (PI) after review of 24-hour safety data from that subject and available safety data from all other subjects.

With the intent of treating subjects with the lowest dose that is safe and tolerable and which has potential for efficacy, dose modification (either an increase to 3 mg/kg or a decrease to 0.3 or 1 mg/kg) may be proposed for individual subject(s) throughout the study, following ongoing evaluation of safety and tolerability data as well as biomarker and response to treatment data. Dose reductions can be made at any point during the study, but dose escalation cannot occur before completion of at least 12 weeks of dosing.

[figure not shown]
After a minimum of 12 weeks of dosing at 1 mg/kg, a review of safety, tolerability, and PD data from each subject will be conducted by the Sponsor in consultation with the PI to determine whether it is appropriate to escalate the dose to 3 mg/kg for that individual subject. Dose frequency (e.g., weekly) modifications may also be considered by the Sponsor after consultation with the SRC and PI, based a review of safety, tolerability, and response to treatment data and with consideration of any other available data on SBC-103.

Safety, PK and PD/efficacy assessments will be performed in all subjects throughout the study.

[figure not shown]
At least 4 weeks after a subject's last dose of SBC-103 is administered in this study, the subject (or the subject's parent or caregiver) will receive a follow-up phone call to assess AEs and concomitant medications unless the subject has a scheduled follow-up study visit.

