As indicated in Figure 1, the planned total duration of the study is approximately 164 weeks. This will include a Screening period that will last up to 4 weeks, an initial study treatment period of 12 weeks at 1 mg/kg, 144 weeks of treatment at up to 3 mg/kg, and a 4-week follow-up period after the last dose is administered.

Figure 1: NGLU-CL01-T Study Schematic

Key: qow = every other week; MRI = magnetic resonance imaging.

DO NOT COPY OR DISTRIBUTE WITHOUT PERMISSION FROM ALEXION

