3.3.2 Decision for Dose Escalation Within a Subject after 12 Weeks of Treatment

Considering the potential for immunogenicity with a protein product, evaluation of the safety and tolerability following multiple rather than single doses prior to escalation is important (see Section 1.3). Therefore, the decision to escalate to 3 mg/kg will be made by the Sponsor and PI only after review of safety, tolerability and PD data from each subject after they have completed a minimum of 12 weeks of treatment. This data review will include HS data from CSF evaluation at 12 weeks and the HS data from serum and urine samples every 4 weeks, along with multiple dose safety and tolerability data.

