5.1.7 Vital Signs and Electrocardiogram

Vital signs, including pulse rate, respiratory rate, systolic and diastolic blood pressure, and body temperature will be taken at the time points specified in the SOA in accordance with local institutional procedures. On Day 1, vital signs will be taken prior to hospital discharge. During dosing visits, vital signs will be taken within approximately 30 minutes before dosing with SBC-103, approximately every 15 minutes during infusion and approximately every 15 minutes for 2 hours after completion of the infusion. Vital signs should also be obtained after the lumbar puncture is completed as per the standard of care. The duration of post-infusion vital signs monitoring may be shortened to 1 hour starting with Week 54, provided that there is no occurrence of IARs during the infusion.

Every effort will be made to collect a 12-lead ECG during the time points specified in the SOA in accordance with local institutional procedures. 12-lead ECGs will be collected in triplicate for the first 6 months. ECGs will be reviewed by the Investigator, or designee, and any abnormalities will be specified as clinically significant or not clinically significant.

Vital signs and ECG monitoring during general anaesthesia prior to the MRI scan will be performed in accordance with local institutional procedures.

Due to the behavioural issues typical of subjects with MPS IIIB, ECG assessments may not be able to be completed, but should be attempted whenever possible.

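### Next-day adverse event contacts are tied to the first four doses, all at 1 mg/kg, and none is repeated when the dose is raised to 3 mg/kg

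*Protocol*

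**What the plan says.** **Early contacts.** Protocol Section 3.1 keeps every subject in hospital for 24 hours after the first dose, and Section 5.2.5 adds calls "within 24 hours after each of the subject's second, third, and fourth doses to assess AEs". The Schedule of Assessments (Appendix A) marks these calls at Weeks 2, 4 and 6. The only other call comes at least 4 weeks after the last dose.

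**Escalation.** All subjects start at 1 mg/kg every other week, and "dose escalation cannot occur before completion of at least 12 weeks of dosing". Section 3.1 describes "an initial study treatment period of 12 weeks at 1 mg/kg, 144 weeks of treatment at up to 3 mg/kg". For the escalation decision, Section 3.3.2 states: "This data review will include HS data from CSF evaluation at 12 weeks". SAP Section 7 reports that every subject was escalated to 3 mg/kg after the first 12 weeks.

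**Observation after each infusion.** Section 5.1.7 schedules vital signs "approximately every 15 minutes for 2 hours after completion of the infusion". From Week 54 this may be cut to 1 hour if no IAR occurred during the infusion.

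**IAR window.** Section 7.1.3 counts an event as an IAR if it is at least possibly related and starts during the infusion or in the 4 hours after it. SAP Section 7.3.2.5.2 uses the same window.

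**The concern.** The extra contacts follow the dose number and not the dose level. Section 3.3.1 justifies the first-dose stay by limited human experience with the product. Section 1.4 reports human dosing only at 0.3 and 1 mg/kg as of 30 April 2015, so that reason applies at least as much to the first infusions at 3 mg/kg. Section 1.5.2 adds that anti-drug antibodies, which may be present by then, can be associated with a higher risk of IARs.

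At stake is how soon a reaction that begins after the child has gone home becomes known. Unless the caregiver reports it, the first scheduled question comes at the next visit, which is the day of the next infusion. Recall of onset time, which decides whether an event falls inside the 4-hour window, may be poorer by then. If the reaction was severe, the required review would begin on the day the infusion was due.

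**Working it through.** **Inputs**

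- Dosing every other week, Day 0 to Week 156 (Section 6.1 and Appendix A), so dose d falls at Week 2(d − 1).
- Yardstick: 4 hours after the end of infusion (Section 7.1.3).
- Routine vital signs: 2 hours, or 1 hour allowed from Week 54 (Section 5.1.7).
- Pharmacokinetic (PK) samples after infusion (Table 2, Section 5.2.1.2): a "4 hours (±5 minutes") sample at Day 0 and Weeks 12 and 24, with later samples to 24 hours (Day 0 and Week 24; the 24-hour sample may be omitted) or 6 hours (Week 12). Weeks 52, 104 and 156 are also sampled to 6 hours. Weeks 78 and 130 have a pre-infusion sample only.
- Interval between infusions: 14 ± 5 days, with a minimum of 10 (Section 6.1).

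**The plan's own schedule.** Doses 2, 3 and 4 fall at Weeks 2(2 − 1) = 2, 2(3 − 1) = 4 and 2(4 − 1) = 6. This matches Appendix A.

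**Earliest 3 mg/kg infusion.** Week 12 is dose 7 and Week 14 is dose 8. Read literally, Section 3.1 allows Week 12. Because the review uses the Week 12 CSF result, Week 14 is the earliest practical start.

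**Infusions with scheduled contact that can reach 4 hours before the next visit.** These are Day 0 (stay), Weeks 2, 4 and 6 (calls), and Weeks 12, 24, 52, 104 and 156 (PK). The first four infusions at each dose then give:

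| Dose and start | Infusions | Can reach 4 h | Certain to reach 4 h |
|---|---|---|---|
| 1 mg/kg, Day 0 | Day 0, Weeks 2, 4, 6 | 4/4 | 1/4 |
| 3 mg/kg, Week 12 | Weeks 12, 14, 16, 18 | 1/4 | 1/4 |
| 3 mg/kg, Week 14 | Weeks 14, 16, 18, 20 | 0/4 | 0/4 |

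The last two columns differ at 1 mg/kg because a call made within 24 hours could come before 4 hours have passed.

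**Later starts.** A Week 16 start gives 0/4, and Weeks 18 to 24 give 1/4 each. No start from Week 12 to Week 150 gives more than 1/4.

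**Whole 3 mg/kg period, Week 14 start.** Infusions: (156 − 14)/2 + 1 = 72. Covered: Weeks 24, 52, 104 and 156, so 4/72. The first of these, Week 24, is the sixth infusion at 3 mg/kg.

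**Delay to the next scheduled question.** Without a call: 14 − 5 = 9 days, raised to the minimum of 10, up to 14 + 5 = 19 days. With a call: at most 1 day.

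**The case against.** The timing by dose number has a rationale. Clinical signs in animals "were noted generally after the third or fourth dose of SBC-103", so calls after the early doses make sense and should stay. Escalation is not like a first exposure: it follows at least 12 weeks of dosing and an individual review, and requires that 1 mg/kg was well tolerated (Section 6.1). Each 3 mg/kg infusion is supervised, with vital signs every 15 minutes, and Section 1.4 describes IARs as reactions "which typically occur either during, or within 2 hours following completion of the infusion". All of this stands, and it is why the effect is probably small. None of it gives a reason to omit calls at escalation.

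Three stronger readings are tempting, and the documents support none of them.

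- *A firm contrast of 4/4 against 0/4.* Three of the four 1 mg/kg contacts are calls that need not reach 4 hours. Counting only contact that is certain, the contrast is 1/4 against 0/4 for a Week 14 start and 1/4 against 1/4 for a Week 12 start.
- *Re-dosing without review.* Section 7.3 requires specific questioning about adverse events at each contact, which includes the next infusion visit. Section 6.2.1 bars treatment after a severe IAR until the Sponsor and Principal Investigator have reviewed it. Pre-treatment after a mild reaction is given about 1.5 hours before the next infusion in any case (Table 4). What remains is a possible late postponement.
- *A biased comparison between doses.* Protocol Section 8.4 foresaw IARs tabulated by dose, but SAP Section 7 presents summaries under 3 mg/kg alone, whatever dose was given at the time. No such comparison is planned.

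**Conclusion.** The point holds as a minor gap in safety follow-up. The early stay and calls all fall at 1 mg/kg, and nothing equivalent is scheduled when the dose triples. Scheduled contact reaching 4 hours covers 0/4 (Week 14 start) or 1/4 (Week 12 start) of the first four 3 mg/kg infusions. At 1 mg/kg it covers up to 4/4, of which one is certain. A reaction after discharge may be learned of 10 to 19 days later instead of after about 1 day.

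This assumes dosing every other week without a run of missed infusions, and that adverse events are asked about before the next infusion starts; Section 7.3 says only at each contact. No discharge time is stated, so longer stays at the site's discretion are not counted. The documents give no rate of IARs starting between 2 and 4 hours, so the number of reactions affected cannot be estimated.

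**What to change.** In Section 5.2.5, keep the calls after doses 2 to 4 and extend the rule, for example: *Call the subject, parent or caregiver more than 4 hours and no later than 24 hours after the end of infusion, following doses 2, 3 and 4 and following each of the first four infusions at any increased dose, to ask about AEs.* Add the calls to the telephone row in Appendix A: Weeks 14, 16, 18 and 20 when 3 mg/kg starts at Week 14.

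**Gain.** For a Week 14 start, coverage of the first four 3 mg/kg infusions rises from 0/4 to 4/4. Over all planned 3 mg/kg infusions it rises only from 4/72 to (4 + 4)/72 = 8/72.

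**Cost.** Four calls per subject per dose increase, so 5 × 4 = 20 for five subjects escalated once, with no new procedure. The calls depend on caregiver report.

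SAP Section 4 records that development was stopped on 11 July 2017, so this concerns the plan as written.
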